E5501/avatrombopag (formerly known as AKR-501 monomaleate and YM477) is an orally administered, small molecule c-Mpl receptor agonist that mimics the biological effects of TPO in vitro and in vivo. Thrombopoietin, the principal physiologic regulator of platelet production, exerts its effect on megakaryocytopoiesis and thrombocytopoiesis via binding and activation of the c-Mpl receptor, which is expressed on hematopoietic stem cells, on cells of the megakaryocytic lineage, and on platelets. Like TPO, avatrombopag also binds to the human c-Mpl receptor and affects signal transduction through the induction of downstream signaling, thereby enhancing human megakaryocytic proliferation and differentiation.

A proof of concept (POC) study (E5501-G000-202) has demonstrated the efficacy, safety, and tolerability of avatrombopag in elevating platelet counts in this group of patients with

thrombocytopenia associated with liver disease prior to elective procedures. Modeling and simulation based on a final pharmacokinetic (PK)/pharmacodynamic (PD) model, of the POC study data, allowed an optimal dosing regimen for Phase 3 to be identified. These simulations showed that the achievement of the appropriate platelet count and a high response rate is affected by baseline platelet count and that dosing avatrombopag is best stratified by baseline platelet count. The simulations also demonstrated that there is no advantage in having a loading dose as was used in the POC study. These simulations have been important because in the POC study the primary endpoint only related to elevation in platelet count, whereas in Phase 3 the primary endpoint will link to the clinical endpoint of platelet transfusion.

The current study will evaluate avatrombopag in the treatment of thrombocytopenia associated with liver disease prior to an elective procedure to reduce the need for platelet transfusions due to procedural and postprocedural bleeding complications.

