#### 9.3.1 Inclusion Criteria

Subjects must meet all of the following criteria to be included in this study:

1. Subjects  $\geq 18$  years of age at Screening with chronic liver disease
2. Subjects who have a mean baseline platelet count of  $< 50 \times 10^9/L$ . Platelet counts must be measured on 2 separate occasions, during the Screening Period and at Baseline, and must be performed at least 1 day apart with neither platelet count  $> 60 \times 10^9/L$ . The mean of these 2 platelet counts (mean baseline platelet count) will be used for entry criteria and for assignment to the low or high baseline platelet count cohort.
3. Subjects scheduled to undergo a permitted elective procedure and who, in the opinion of the investigator, will otherwise require a platelet transfusion to address a risk of bleeding associated with the procedure unless there is a clinically significant increase in platelet count from baseline (revised per Amendments 02 and 03)
4. Model For End-stage Liver Disease (MELD) score  $\leq 24$  at Screening
5. If taking inhibitors of P glycoprotein (P-gp), except for verapamil, dose must be stable for 7 days prior to Screening (see [Appendix 2](#) for the list of P-gp Inhibitors)
6. Provide written informed consent
7. Willing and able to comply with all aspects of the protocol

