#### **9.4.4 Selection of Doses in the Study**

Dose selection has been carefully focused on seeking to maintain an appropriate risk:benefit ratio balance in this patient population, removing the requirement for platelet transfusion, or any rescue procedure for bleeding, while minimizing the risk of thromboembolic events. The selected doses, based on modeling and simulation of the E5501-G000-202 study data, are aimed at achieving sufficient efficacy (eliminating the need for platelet transfusion) while specifically limiting the proportion of subjects achieving platelet counts  $>200 \times 10^9/L$  to less than 2%.

The current study design employs a dosing regimen according to baseline platelet count that is anticipated to lead to a similar overall rise in platelet counts irrespective of baseline platelet count.

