### EXPLORATORY EFFICACY ANALYSES

The following efficacy variables are considered exploratory:

- Platelet count and change from baseline in platelet count at each visit
- Proportion of subjects who achieve platelet count of  $\geq 50 \times 10^9/L$ ,  $\geq 75 \times 10^9/L$ , or  $\geq 200 \times 10^9/L$  at each visit
- Number of platelet units used per platelet transfusion episode
- Severity of bleeding events assessed by WHO bleeding score and BARC bleeding scale
- Proportion of subjects with a WHO bleeding score  $\geq 2$  after randomization and up to 7 days following an elective procedure (revised per Amendment 04)

In general, the continuous variables will be analyzed within an analysis of covariance framework or Wilcoxon rank sum test, as appropriate. Categorical variables will be analyzed using CMH, Chi-square or Fisher's exact test. Additional analysis may be performed as needed using appropriate statistical methodologies as specified in the SAP.

Subgroup analyses will be performed on the primary efficacy variable, including age group ( $< 65$  and  $\geq 65$  years old); sex (male and female); race (white, black, asian and other); geographic region; bleeding risk associated with the elective procedure (low, moderate, or high based on Amendment 02 categorization); MELD score ( $< 10$ , 10-14, and  $> 14$ ); and CTP grade (A, B, and C). Additional subgroups may be explored, if deemed appropriate.

No adjustment for multiplicity is planned for exploratory, subgroup and sensitivity analyses.

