5.3.2 Adjustments for Covariates

The primary efficacy endpoint, the proportion of subjects without platelet transfusion or any rescue procedure for bleeding, and the first secondary efficacy endpoint, proportion of subjects with platelet count $\geq 50 \times 10^9/L$ on Procedure Day, will be analysed separately within each

baseline platelet count cohort ($<40 \times 10^9/L$ or from 40 to $<50 \times 10^9/L$) using the Cochran-Mantel-Haenszel (CMH) test adjusting for the risk of bleeding associated with the elective procedure (low, moderate, or high based on Amendment 02 categorization). Since the HCC status is included in the randomization stratification for safety purposes only, not for efficacy consideration, HCC will not be included in the CMH model for the primary efficacy analysis.

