5.4.1 Primary Efficacy Analyses

The primary efficacy variable is the proportion of subjects who do not require a platelet transfusion or any rescue procedure for bleeding after randomization and up to 7 days following an elective procedure.

The null hypothesis is that the proportion of subjects not requiring a platelet transfusion or any rescue procedure for bleeding after randomization and up to 7 days following an elective procedure is the same between the avatrombopag and placebo treatment groups. The corresponding alternative hypothesis is that the proportion of subjects not requiring a platelet transfusion or any rescue procedure for bleeding after randomization and up to 7 days following an elective procedure is not the same between avatrombopag and placebo. This hypothesis will be tested separately with each baseline platelet count cohort.

The proportion of subjects not requiring a platelet transfusion or any rescue procedure for bleeding will be tested between the individual avatrombopag treatment group (40 or 60mg) and matching placebo within each baseline platelet count cohort ($<40 \times 10^9/L$ or from 40 to $<50 \times 10^9/L$), each at a significance level of $\alpha=0.05$ using the generalized Cochran Mantel Haenszel (CMH) test adjusting for the risk of bleeding associated with the elective procedure (low, moderate, or high based on Amendment 02 categorization).

- For subjects with platelet count $<40 \times 10^9/L$ at baseline, the treatment comparison will be carried out between the 60 mg avatrombopag treatment group (Group A) versus matching placebo (Group B).
- For subjects with platelet count from 40 to $<50 \times 10^9/L$ at baseline, the treatment comparison will be carried out between the 40 mg avatrombopag treatment group (Group C) versus matching placebo (Group D).

This study will be considered as positive if statistical significance is achieved for primary efficacy endpoints for both baseline platelet count cohorts.

The 95% CI for the proportion of subjects not requiring a platelet transfusion or any rescue procedure for bleeding will be calculated for each treatment group within each baseline platelet count cohort. In addition, the 95% CI for the difference between avatrombopag and matching placebo will also be provided within each baseline platelet count cohort using normal approximation method.

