5.4.2 Secondary Efficacy Analyses

There are 2 secondary efficacy endpoints in this study:

- Proportion of responders, defined as subjects who achieve target platelet counts of $\geq 50 \times 10^9/L$ on Procedure Day (prior to receiving a platelet transfusion or undergoing the elective procedure)
- Change from baseline in platelet count on Procedure Day (prior to receiving a platelet transfusion or undergoing the elective procedure)

The analysis of the secondary efficacy variables, as defined above, will proceed following a sequential gatekeeping testing procedure to control the family-wise Type I error rate at a significance level of $\alpha=0.05$.

5.4.2.1 Proportion of subjects achieved platelet counts of $\geq 50 \times 10^9/L$ on the Procedure Day

The proportion of subjects who achieve platelet counts of $\geq 50 \times 10^9/L$ on the Procedure Day will be analyzed first.

The proportion of subjects with platelet counts of $\geq 50 \times 10^9/L$ on the Procedure Day will be tested between the individual avatrombopag treatment group (40 or 60mg) and matching placebo separately within each baseline platelet count cohort ($< 40 \times 10^9/L$ or from 40 to $< 50 \times 10^9/L$), each at a significance level of $\alpha=0.05$ using the generalized CMH test adjusting for the risk of bleeding associated with the elective procedure (low, moderate, or high based on Amendment 02 categorization).

The 95% CI for the proportion of subjects with platelet counts of $\geq 50 \times 10^9/L$ on the Procedure Day will be calculated for each treatment group within each baseline platelet count cohort. In addition, the 95% CI for the difference between avatrombopag and placebo will also be provided within each baseline platelet count cohort using normal approximation method.

Subjects with missing platelet count on Procedure Day will be considered as not achieving the platelet count of $\geq 50 \times 10^9/L$ for this analysis.

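### Within each cohort the primary and first secondary tests leave out baseline platelet count; adjusting for it would be a modest gain in efficiency, not the repair of an error

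*SAP*

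**What the plan says.** The primary comparison is made cohort by cohort (SAP 5.4.1: "This hypothesis will be tested separately with each baseline platelet count cohort"). Within a cohort the CMH test has one stratification factor, procedural bleeding risk in three levels: SAP 5.4.1 specifies a "test adjusting for the risk of bleeding associated with the elective procedure (low, moderate, or high based on Amendment 02 categorization"). SAP 5.4.2.1 treats the proportion reaching 50 × 10⁹/L on Procedure Day in the same way, "using the generalized CMH test adjusting for the risk of bleeding associated with the elective procedure". SAP 5.3.2 explains one omission, that "HCC will not be included in the CMH model for the primary efficacy analysis", because HCC was a stratification factor for safety only. It gives no reason for omitting baseline count within the cohort. None of the sensitivity analyses listed in SAP 5.4.1.1 adds baseline count, and the subgroup list in SAP 5.4.1.2 does not include it.

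Protocol 7.1 reports simulations showing that "the achievement of the appropriate platelet count and a high response rate is affected by baseline platelet count", and the same sentence goes on to conclude that dosing should be stratified by baseline count. The design follows that conclusion with two cohorts, each with its own dose and its own placebo group. Protocol 9.4.4 describes a regimen "anticipated to lead to a similar overall rise in platelet counts irrespective of baseline" count. The covariate is collected by design (Protocol 9.3.1): "The mean of these 2 platelet counts (mean baseline platelet count) will be used for entry criteria and for assignment" to cohort.

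**The concern.** Splitting at 40 uses baseline count only coarsely. If the rise is similar for everyone, the Procedure Day count still moves with the baseline count. In the lower cohort a subject starting at 20 needs 50 − 20 = 30 to reach the threshold of the first secondary endpoint, and a subject starting at 39 needs 50 − 39 = 11. Transfusion decisions are guided by platelet count (Protocol 7.1), so some of this dependence plausibly carries over to the primary endpoint. Bleeding risk is a property of the procedure and does not stand in for it.

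Two things are at stake. Variation that baseline count could explain stays in the error term. And no listed analysis shows whether a chance imbalance in baseline count between 67 and 33 subjects has moved the estimate. Both cohorts must be significant for the study to be positive, so a loss in either one matters.

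**Working it through.** **Inputs from the documents.** Per cohort: 67 avatrombopag and 33 placebo, 18% placebo response, a difference of 35 points (so 53% v 18%), two-sided α = 0.05, power above 90% by Fisher's exact test (SAP 4). The documents give no within-cohort association between baseline count and response, and no SD for baseline count or for the rise. Those are assumed below.

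**Step 1: the plan's own figure.** Exact power = Σ Bin(x₁; 67, 0.53) · Bin(x₀; 33, 0.18) over all (x₁, x₀) with Fisher p ≤ 0.05. This gives 92.6%, in line with the plan. If the cohorts are independent, the chance that both succeed is 0.926² ≈ 0.86.

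**Step 2: how the gain depends on prognostic strength.** One cohort was simulated with the marginal response rates fixed, risk strata assumed 60/20/20, no effect of risk on response, and 4,000 runs. CMH by risk was compared with a logistic score test adding continuous baseline count. Strength is expressed as the AUC of baseline count for response on placebo. The variance ratio is that of the risk difference, adjusted over unadjusted, at the planned effect.

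| AUC (assumed) | 53% v 18%: CMH → adjusted | 43% v 18%: CMH → adjusted | Variance ratio |
|---|---|---|---|
| 0.50 | 93.7 → 93.7% | 71.4 → 72.1% | 1.02 |
| 0.57 | 93.9 → 94.3% | 70.8 → 72.1% | 1.01 |
| 0.64 | 93.6 → 95.0% | 71.4 → 73.8% | 0.98 |
| 0.70 | 93.4 → 95.7% | 72.4 → 76.7% | 0.93 |
| 0.75 | 94.0 → 97.2% | 70.4 → 79.0% | 0.88 |
| 0.82 | 93.4 → 98.6% | 70.1 → 85.2% | 0.78 |

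Monte Carlo error is about 0.2 to 0.8 points. Under the null, CMH rejected in 4.4–4.6% of runs and the logistic score test in 5.0–5.7%, so part of the apparent gain is size. This table shows the shape of the dependence; it does not measure the gain from the method recommended here.

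**Step 3: the recommended test.** In randomisation-based adjustment, d is the stratum-weighted difference in response and u the stratum-weighted difference in mean baseline count. The adjusted difference is d − V_du V_uu⁻¹ u, with variance V_dd − V_du V_uu⁻¹ V_ud. It was simulated at 67/33 and 53% v 18%, with response taken as baseline plus rise ≥ 50, assumed rise SDs (15–25 on drug and 8–12 on placebo in the runs that state them) and 4,000 or 6,000 runs per scenario.

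- Size: 4.7–5.3%, against 4.5–5.3% for CMH in the runs that report both.
- Lower cohort: gain over CMH of 0.5–2.0, 0.8–1.9 and 0.8–2.4 points in three sets of runs.
- Higher cohort: 0.2–0.5, 0.1–0.5 and 0–0.6 points.
- If 20% of outcomes are assumed unrelated to platelet count: 0.2–1.0 points in the lower cohort and −0.1 to 0.1 in the higher.

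In terms of winning both cohorts, take CMH power as 94% in each and the cohorts as independent. Then 0.94 × 0.94 = 0.884. It becomes 0.945 × 0.940 = 0.888 at the low end and 0.965 × 0.946 = 0.913 at the high end, a gain of roughly 0.5 to 3 points.

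**Step 4: first secondary endpoint.** Take Procedure Day count = baseline + rise, with baseline uniform on 20–40 or 40–50, placebo rise mean 2 (SD 6 to 15), and active rise mean 20 (SD 15) or 30 (SD 25), all assumed. The approximate variance reduction is (v₀R₀² + v₁R₁²)/(v₀ + v₁), with v₀ = p₀(1−p₀)/33 and v₁ = p₁(1−p₁)/67. Example, lower cohort: p₀ = 0.013, R₀² = 0.022, p₁ = 0.50, R₁² = 0.088. Then v₀ = 0.00039, v₁ = 0.00373, and the reduction is about 0.08. Across the settings it is about 3–8% in the lower cohort and 2–9% in the higher.

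**The case against.** A reader might infer that the primary analysis is biased or invalid, or that it ignores baseline count. The documents do not support this. CMH stratified by a randomisation factor holds its level, randomisation makes a chance baseline imbalance part of the error the test already allows for, and baseline count is used through the cohorts, their doses and their separate placebo groups.

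A reader might also take Protocol 7.1 to say that baseline count determines response, so that precision is certainly being thrown away. It says only that response is affected by baseline, across the whole range, and gives no within-cohort effect. The upper cohort is only 10 × 10⁹/L wide.

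The simulated response in steps 3 and 4 is a platelet threshold, which is the first secondary endpoint. The primary endpoint also depends on the investigator's judgement about transfusion, on rescue procedures for bleeding, and on missing outcomes being counted as transfused. For the primary test the step 3 figures are therefore closer to a ceiling. The larger gains in step 2 need AUCs of 0.75 or more, which nothing in the documents supports.

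The protocol's mention that "the continuous variables will be analyzed within an analysis of covariance framework or Wilcoxon rank sum test" lends little support, since it concerns continuous exploratory variables and not a binary primary test. SAP 5.4.1.1 also leaves room for additional sensitivity analyses.

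All of this stands, and it limits the point to efficiency. What remains is that a plausible prognostic covariate, available in essentially every randomised subject, is left out without a stated reason, and that an optional later analysis carries less weight than one named before unblinding.

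**Conclusion.** The point holds as a modest improvement in efficiency. For the recommended test the gain is roughly 0.5 to 2.5 points of power in the lower cohort and 0 to 0.6 in the higher, with no material cost in size. These figures rest on assumed baseline distributions, rise SDs and risk-stratum shares. The gain shrinks if the primary outcome follows platelet count less closely. If baseline is not prognostic within the cohort, there is no gain and the variance may rise by 1–2%. The planned tests remain valid and the sample size calculation stands.

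**What to change.** Before unblinding, add to SAP 5.3.2, 5.4.1 and 5.4.2.1 a randomisation-based covariate-adjusted CMH analysis within each cohort. Keep the bleeding-risk strata, enter baseline platelet count as a continuous covariate, and report the adjusted risk difference with its 95% CI. This is preferable to a logistic model, whose score test ran slightly above its level and whose coefficient is a conditional odds ratio that does not match the planned risk difference. It is also preferable to crossing risk with a median split of baseline, which cost about 1 point of power when baseline was not prognostic (93.7% to 92.8% at the planned effect).

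Name the covariate: the mean of the two pre-randomisation local-laboratory counts used for cohort assignment, and not the last visit on or before Study Day 1 that SAP 8.1 defines for by-visit summaries.

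Then choose its role. The lighter option is a named sensitivity analysis in SAP 5.4.1.1, with a matching sentence in 5.4.2.1, and the CMH tests unchanged. If it is to replace the primary test, Protocol 9.7.1.6 and the synopsis must be aligned as well. The cost is SAP wording, possibly protocol wording, and a little extra programming. No new data are needed.

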4 DETERMINATION OF SAMPLE SIZE

The proposed sample size was based on comparisons of the primary efficacy variable, with the response rate defined as the proportion of subjects who do not require a platelet transfusion or any rescue procedure for bleeding after randomization and up to 7 days following an elective procedure. Based on clinical opinion and the published results of a similar compound in adults with thrombocytopenia associated with liver disease (ELtrombopag EValuated for its Ability to overcome Thrombocytopenia and Enable procedures [ELEVATE] study [Afdahl, 2012])², the response rate in the placebo group is assumed to be 18%. Within each baseline platelet count cohort, a sample size of 100 randomized subjects, 67 subjects for avatrombopag and 33 subjects for placebo, would have greater than 90% power to detect an absolute difference of 35% between the avatrombopag response rate and the placebo response rate assuming 18% response rate for placebo using Fisher's Exact tests with a 2-sided $\alpha=0.05$. The hypothesized treatment group difference was based on platelet count changes found in the Phase 2 study (E5501-G000-202) and dose-response modeling using data from that study and others in the project development. Based on the baseline data in the Phase 2 study and assuming these were projected to be similar for this study, it was anticipated that this study would enroll roughly half of the total number of subjects in each of the 2 baseline platelet count cohorts to make the total sample size of 200 randomized subjects, 133 subjects for avatrombopag and 67 subjects for placebo.

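### The normal-approximation intervals for the primary and first secondary differences cover slightly less than 95%, tend to set the lower limit too high, and do not match the stratified CMH test

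*SAP*

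**What the plan says.** SAP 5.4.1 tests the primary endpoint within each platelet cohort by the "generalized Cochran Mantel Haenszel (CMH) test adjusting for the risk of bleeding associated with the elective procedure", with three risk levels. The interval for the difference is then "provided within each baseline platelet count cohort using normal approximation method". SAP 5.4.2.1 repeats the pairing for platelet count of at least 50 on Procedure Day: the test is done "using the generalized CMH test adjusting for the risk of bleeding associated with the elective procedure", and "the 95% CI for the difference between avatrombopag and placebo will also be provided within each baseline platelet count cohort using normal approximation method".

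Neither section names strata, weights or a continuity correction for the interval. Protocol 9.7.1.6 promises an interval for the primary difference and names no method, so the choice is made in the SAP alone. The sensitivity analyses in SAP 5.4.1.1 include Fisher's exact test, which changes the test; no alternative interval is listed.

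SAP 4 plans, per cohort, "67 subjects for avatrombopag and 33 subjects for placebo" to detect "an absolute difference of 35% between the avatrombopag response rate and the placebo response rate" with placebo at 18%, that is 53% v 18%.

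**The concern.** The Wald interval estimates each arm's variance from that arm's observed rate. When placebo response is well below 50%, a chance shortage of placebo responders does two things at once: it raises the estimated difference and it shrinks the estimated variance. The interval is therefore narrowest when the estimate is too high, and the lower limit tends to sit too high. With only 33 placebo subjects per cohort this may not be negligible.

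The second issue is coherence. The p-value comes from a stratified analysis and the interval apparently from a crude one, so a report could show an interval that excludes zero beside a non-significant test. At stake is the accuracy of the reported effect size, chiefly its lower limit.

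**Working it through.** **Inputs.** From SAP 4: n1 = 67, n0 = 33, p0 = 0.18, p1 = 0.18 + 0.35 = 0.53. The documents give no response rates for the first secondary endpoint and no stratum sizes, only that the low-risk group is at most 60% and the high-risk group at least 10% of subjects. Assumed stratum sizes (low/moderate/high): 40/13/14 v 20/6/7, and 40/20/7 v 20/10/3.

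**The plan's own figure.** Summing the two binomials over all outcomes where Fisher's two-sided p is at most 0.05 gives power of 92.6%, which agrees with the stated figure of more than 90%.

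**Wald coverage at the planned rates.** The interval is d ± 1.96 × sqrt[a(1−a)/n1 + b(1−b)/n0], where a and b are the observed rates and d = a − b. Exact enumeration over Binomial(67, p1) × Binomial(33, p0):

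| Interval, 53% v 18% | Coverage | Lower limit too high | Upper limit too low |
|---|---|---|---|
| Wald | 94.0% | 4.1% | 1.9% |
| Miettinen-Nurminen | 94.9% | 2.3% | 2.8% |
| Newcombe | 94.9% | 1.7% | 3.4% |

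Over placebo rates of 3–40% and differences of 15–55 points, Wald coverage averages 94.1% (range 93.1–95.4%). It is below 95% at 98% of the points, and the lower-side miss is the larger at 98% of them.

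**One data set, 36/67 v 6/33.** a = 0.5373, b = 0.1818, d = 0.3555. The variance is 0.2486/67 + 0.1488/33 = 0.00371 + 0.00451 = 0.00822, so SE = 0.0907 and 1.96 × SE = 0.1777. Wald gives 17.8 to 53.3 points, Miettinen-Nurminen about 15.7 to 51.3, and Newcombe 15.5 to 50.4.

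**First secondary endpoint (Wald, 67 v 33).** All rates are illustrative. The first pair is the Phase 2 result in protocol 7.1.2.3, which is for a different platelet endpoint.

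| Rates | Coverage | Lower limit too high |
|---|---|---|
| 48.4% v 8.1% | 94.1% | 4.0% |
| 65% v 5% | 94.3% | 4.2% |
| 80% v 5% | 93.3% | 5.6% |
| 90% v 5% | 92.2% | 7.0% |

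A placebo rate near zero is not enough by itself. Coverage falls clearly only when the active rate is also high, because the active arm's variance estimate then shrinks along with its overestimation.

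**Agreement with CMH (400,000 simulated trials per setting, three strata).** With equal rates across strata, crude Wald excludes zero while CMH is not significant in 1.4% of trials at a 35-point difference and 5.5% at 25 points. With 18% in both arms, Wald excludes zero in about 6.0% of trials and CMH rejects in 4.9%.

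**Does stratifying alone help?** The Mantel-Haenszel difference with a normal-approximation (Sato) interval covers 94.0% (4.1% / 1.9%) at the planned rates, so it does not.

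**Stratified score interval.** In stratum k let N = n1 + n0 and w = n1·n0/N. The interval holds every δ for which |Σ w(d − δ)| ≤ 1.96 × sqrt(Σ w²V), where V = [q1(1−q1)/n1 + q0(1−q0)/n0] × N/(N−1) and q1, q0 are the maximum-likelihood rates subject to q1 − q0 = δ. At δ = 0 both rates equal the pooled q, and w²V = n1·n0·q(1−q)/(N−1), which is the CMH variance. The interval therefore excludes zero exactly when the CMH test without continuity correction is significant. In 200,000 simulated trials per setting it covered 94.9% at the planned rates (2.2% / 2.8%) and 95.0–95.1% at 48.4% v 8.1%, with no disagreements with CMH.

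**The case against.** The strongest reply is that no decision uses this interval. SAP 5.3.3 rests success and the gate to each secondary endpoint on the CMH tests, and neither document sets a margin or a minimum-benefit threshold for the lower limit. The shift at the planned rates is about two points (17.8 − 15.7 = 2.1) on an interval about 35 points wide. A crude difference beside a stratified test is common in reports. All of this stands, and it limits the point to accuracy of reporting.

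It can also be said that the SAP never calls the interval unstratified. That is right: the crude form is the natural reading, not a stated fact. But the other reading, a Mantel-Haenszel difference with a normal-approximation interval, has the same coverage at the planned rates, so the coverage finding does not depend on it.

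The mismatch with CMH shrinks if response varies between risk strata. In the heterogeneous settings simulated near the planned effect, Wald excluded zero without CMH significance in 0.3–0.8% of trials. Crude coverage was then 94.5–94.8%, though the lower-limit miss stayed at 3.6–3.8%.

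A reader might infer that the first secondary endpoint must be worse than the primary because its placebo rate could be very low. The documents give no rates for it, and at the nearest figures they contain the shortfall is about the same.

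**Conclusion.** The point holds as a modest reporting defect. At the plan's own sizes and rates the interval loses about one point of coverage, and about two thirds of its misses (4.1 of 6.0 points) are lower limits that lie above the true difference. The primary result rests only on SAP 4. The first secondary figures and the agreement rates rest on assumed response rates and stratum sizes.

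Two stronger readings are not supported. A reader might infer that the study could be declared positive wrongly; it could not on this ground, since the interval plays no part in the success rule. A reader might also extend the criticism to the single-arm intervals; the SAP names no method for those, and nothing here shows them to be wrong.

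**What to change.** In SAP 5.4.1 and 5.4.2.1, replace the normal approximation for the difference with the Miettinen-Nurminen score interval, stratified by bleeding risk (low, moderate, high) with Mantel-Haenszel weights. Settle this before unblinding so that the choice cannot follow the data. No protocol change is needed.

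A stratified normal-approximation interval is not a substitute, because it keeps the coverage defect. Newcombe should not be listed as equivalent, because it moves the imbalance to the upper limit: 1.7% / 3.4% at the planned rates and 0.1% / 5.6% at 90% v 5%.

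The cost is one line of SAP wording and a standard software option. Reported lower limits become slightly less favourable, and the unstratified score interval is mildly conservative at extreme rates (96.2% at 90% v 5%).
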